### 9.1.4 Adverse Event Reporting Period

For this study, the study treatment period is defined as 10 days, but subjects will be monitored in the nursing home, hospital, another care facility, or at home directly by study staff or the patient's care providers or by telephone contact by study staff for Day  $180\pm14$ . The adverse event reporting period ends when the subject completes the study at Day  $180\pm14$ .

# 9.1.5 Preexisting Condition

A preexisting condition is one that is present at the start of the study. A preexisting condition will be recorded as an adverse event if the frequency, intensity, or the character of the condition worsens during the study period.

### 9.1.6 Medical History Findings

At screening, any clinically significant abnormality will be recorded as a preexisting condition. At the end of the study, any new clinically significant findings/abnormalities that meet the definition of an adverse event will also be recorded and documented as an adverse event. All admission diagnoses and reasons for hospital admission will be recorded.

# 9.1.7 Post-Study Adverse Event

All unresolved adverse events will be followed by the Principal Investigator until the events are resolved, the subject is lost to follow-up, or the adverse event is otherwise explained. At the last scheduled visit or follow-up telephone call (Day 180±14), the PI will instruct each subject to report, to the PI, any subsequent event(s) that the subject, or the subject's nursing home or personal physician, physician's assistant, or nurse practitioner believes might reasonably be related to participation in this study.

# 9.1.8 Abnormal Laboratory Values

A clinical laboratory abnormality will be documented as an adverse event if it changes from a value within the normal range (or as *per* clinical judgment) before treatment to one outside and worse than the normal range after treatments. Such changes will prompt a repeat test, telephone call to check the subject's status, a repeat visit, and/or referral to the subject's primary care physician.

# 9.1.9 Hospitalization, Prolonged Hospitalization, or Surgery

Any adverse event that results in hospitalization or prolonged hospitalization will be documented and reported as a serious adverse event unless specifically instructed otherwise in this protocol. Any condition responsible for surgery will be documented as an adverse event if the condition meets the criteria for an adverse event.

Neither the condition, hospitalization, prolonged hospitalization, or surgery will be reported as an adverse event in the following circumstances:

The following hospitalizations will not be considered SAE for this study:

- a visit to the emergency department or other hospital department <24 hours, that does not result in admission (unless considered an important medical or life-threatening event).
- elective surgery planned prior to signing consent.
- admissions as *per* protocol for a planned medical/surgical procedure.
- routine health assessment requiring admission for baseline/trending of health status (*e.g.*, routine mammogram).
- medical or surgical admission other than to remedy ill health and planned prior to entry into the study. Appropriate documentation will be obtained in these cases.

# 9.2 Recording of Adverse Events

At each contact with the subject, the study team will seek information on adverse events by specific questioning and, as appropriate, by examination. Information on all adverse events will be recorded immediately in the source document, and also in the appropriate adverse event section of the case report form (CRF) or in a separate adverse event worksheet. All clearly related signs, symptoms, and abnormal diagnostic, laboratory, or procedure results will be

recorded in the source document.

All adverse events occurring during the study period will be recorded. The clinical course of each event will be followed until resolution, stabilization, or until it has been ultimately determined that the study treatment or participation is not the probable cause. Serious adverse events that are still ongoing at the end of the study period will be followed up to determine the final outcome. Any serious adverse event that occurs during the Adverse Event Reporting Period and will be considered to be at least possibly related to the study treatment or study participation will be recorded and reported immediately.

# 9.3 Reporting of Serious Adverse Events and Unanticipated Problems

When a serious adverse event has been identified, the study team will take appropriate action necessary to protect the study participant and then complete the Study Adverse Event Worksheet and log. The Principal Investigator will evaluate the event and determine the necessary follow-up and reporting required. The PI will notify the Sponsor-Investigator within 24 hours of becoming aware of the serious adverse event and report the event to the Mayo Clinic IRB within 5 working days.

# 9.3.1 Principal Investigator Reporting: Notifying the Mayo Clinic IRB

The Principal Investigator will report to the Mayo Clinic IRB any UPIRTSOs and Non-UPIRTSOs according to the Mayo Clinic IRB Policy and Procedures.

Information collected on the adverse event worksheet (and entered in the research database):

- Subject's name:
- Disease/histology (if applicable):
- The date the adverse event occurred:
- Description of the adverse event:
- Relationship of the adverse event to the research: Not Related, Possible, Probable, Definitely Related.
- If the adverse event was expected:
- The severity of the adverse event: Mild, Moderate, Severe.
- If any intervention was necessary/action taken:
- Resolution: (was the incident resolved spontaneously or after discontinuing treatment).
- Date of Resolution:

The Principal Investigator will sign and date the adverse event report when it is reviewed. For this protocol, only directly related SAEs/UPIRTSOs will be reported to the IRB. The Sponsor-Investigator will review all adverse event reports to determine if specific reports need to be made to the FDA.

# 9.3.2 Relationship

The relationship of an AE to the Investigational Drug is a clinical decision by the Principal-Investigator based on all available information at the time of the completion of the CRF and is graded as follows:

0. Not related: a reaction for which sufficient information exists to indicate that the etiology is unrelated to the study drug; the subject did not receive the study medication or the temporal sequence of the AE onset relative to administration of the study medication is not reasonable or the event is clearly related to other factors such as the subject's clinical state, therapeutic intervention or concomitant therapy.

- 1. Possible: a clinical event, including laboratory test abnormality, with a reasonable time sequence to administration of the drug but which could also be explained by concurrent disease or other drugs or chemicals; information on drug withdrawals may be lacking are unclear.
- 2. Probable: a clinical event including laboratory test abnormality, with a reasonable time sequence to administration of the drug, unlikely to be attributed to concurrent disease or other drugs or chemicals and which follows a clinically reasonable response on withdrawal (de-challenge): re-challenge information is not required to fulfil this definition.
- 3. Definitely Related: a reaction that follows a reasonable temporal sequence from administration of the drug, or in which the drug level has been established in body fluids or tissues, that follows a known or expected response pattern to the suspected drug, and that is confirmed by improvement on stopping or reducing the dosage of the drug, and reappearance of the reaction on repeated exposure (re-challenge).

# 9.3.3 Severity

The maximum intensity of an AE during a day should be graded according to the definitions below and recorded in details as indicated on the CRF. If the intensity of an AE changes over a number of days, then separate entries should be made having distinct onset dates.

- 1. Mild: AEs are usually transient, requiring no special treatment, and do not interfere with patient's daily activities.
- 2. Moderate: AEs typically introduce a low level of inconvenience or concern to the patient and may interfere with daily activities, but are usually ameliorated by simple therapeutic measures.
- 3. Severe: AEs interrupt a patient's usual daily activity and traditionally require systemic drug therapy or other treatment.

# 9.4 Sponsor-Investigator Reporting: Notifying the FDA

The Sponsor-Investigator will report to the FDA all unexpected, serious suspected adverse reactions according to the required IND Safety Reporting timelines, formats, and requirements.

Unexpected fatal or life threatening suspected adverse reactions where there is evidence to suggest a causal relationship between the IP and the adverse event will be reported as a serious suspected adverse reaction. This will be reported to the FDA on FDA Form 3500A no later than 7 calendar days after the sponsor-investigator's initial receipt of the information about the event.

Other unexpected serious suspected adverse reactions where there is evidence to suggest a causal relationship between the IP and the adverse event, will be reported as a serious suspected adverse reaction. This will be reported to the FDA on FDA Form 3500A no later than 15 calendar days after the sponsor-investigator's initial receipt of the information about the event.

Any clinically-important increase in the rate of serious suspected adverse reactions over those listed in the protocol or product insert will be reported as a serious suspected adverse reaction. This will be reported to the FDA on FDA Form 3500A no later than 15 calendar days after the sponsor-investigator's initial receipt of the information about the event.

Findings from other studies in human or animals that suggest a significant risk in humans exposed to the drug will be reported. This will be reported to the FDA on FDA Form 3500A, no later than 15 calendar days after the sponsor-investigator's initial receipt of the information about the event.

### 9.5 Unmasking/Unblinding Procedures

The IP blind shall not be broken by the investigator unless information concerning the IP is necessary for the medical treatment of the subject. In the event of a medical emergency, if possible, the sponsor-investigator should be contacted before the IP blind is broken to discuss the need for unblinding.

If the Sponsor-Investigator and PI decides emergency unblinding is medically necessary, the PI needs to contact the Research Pharmacy. The sponsor-investigator must be notified as soon as possible if the IP blind is broken. The date, time, and reason the blind is broken must be recorded in the source documents, CRFs, or Event forms/logs.

# 9.6 Stopping Rules

All patients will be assessed during the 10 days of drug (Fisetin or placebo) administration and during each visit following administration of the drugs. If a severe adverse event occurs at any time during administration of the 10-day drug regimen, a formal review will occur and subsequent patients will be enrolled one at a time using the same regimen. If four or more events accrue, the pilot study will be held and either a potentially alternative dosing regimen considered or discontinuation of the study protocol will occur. Other interventions will be as *per* the direction of the FDA and Mayo (and other participating institutions) IRB.

Toxicity Stopping Rule: The study will be terminated if the number of treatment-related deaths in the patients already registered and treated in the trial exceed 10%.

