#### List of Abbreviations

AE Adverse Event/Adverse Experience

AFFIRM Alleviation by Fisetin of Frailty, Inflammation, and Related Measures Trial

ALT Alanine Aminotransferase

ARDS Acute Respiratory Distress Syndrome

AST Aspartate Aminotransferase

BAP Biospecimens Accessioning and Processing Laboratory

CFR Code of Federal Regulations

CK Creatine Kinase
CoV Coronavirus-19
CRF Case Report Form

CTCAE Common Terminology Criteria for Adverse Events

CVA Cerebrovascular Accident

D Dasatinib

DAMP Damage-Associated Molecular Profile
DSMB Data and Safety Monitoring Board
ECMO Extra-Corporeal Membrane Oxygenation
eGFR Estimated Glomerular Filtration Rate
ESR Erythrocyte Sedimentation Rate
FDA Food and Drug Administration
γ-H2.AX γ-Histone 2.A DNA Damage Foci

GCP Good Clinical Practice

GCSF Granulocyte Colony Stimulating Factor

GMP Good Manufacturing Practice

HIPAA Health Insurance Portability and Accountability Act

HUVEC Human Umbilical Vein Endothelial Cell

IB Investigator's Brochure

IL (e.g., IL-6) Interleukin (e.g., Interleukin-6)

IND Investigational New Drug Application

IP Investigational Product

IPF Idiopathic Pulmonary Fibrosis IRB Institutional Review Board

LAR Legally Authorized Representative

LPS Lipopolysaccharide

MCP-1 Monocyte Chemoattractant Protein-1

MDS Minimal Data Set

MHV Mouse Hepatitis Virus, a Mouse β-Coronavirus

MIP1-α Macrophage Inflammatory Protein 1-α

miRNA Micro-RNA

MMP Matrix Metallopeptidase
MSC Mesenchymal Stem Cell
NME Normal Microbial Experience

PAMP Pathogen-Associated Molecular Profile

PHI Protected Health Information

PI Principal Investigator

Q Quercetin

SA-βGal Senescence-Associated β-Galactosidase

SAE Serious Adverse Event/Serious Adverse Experience

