### 4.4 Early Withdrawal of Subjects

# When and How to Withdraw Subjects

All subjects will be assessed during the initial day of medication administration, subsequent days of medication administration, and all study visits. If a severe adverse event (SAE) occurs at any time during administration of the drug regimen, a formal review will occur. If 4 or more events accrue, the pilot study will be held and either the dosing regimen revised or discontinuation of the study protocol will occur. Other interventions will be as *per* the direction of the Food and Drug Administration (FDA), Mayo Clinic Institutional Review Board (IRB), and policies of the patient's nursing home.

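### The four-event hold in sections 9.6 and 4.4 pools both arms, sets no relatedness condition and uses inconsistent event terms, so COVID-19 progression alone could trigger it without signalling Fisetin harm

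*Combined protocol and SAP*

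**What the plan says.** Section 9.6 has two steps. It opens with "If a severe adverse event occurs at any time during administration of the 10-day drug regimen": a formal review follows, and later patients are enrolled one at a time. Then, "If four or more events accrue, the pilot study will be held", after which "either a potentially alternative dosing regimen considered or discontinuation of the study protocol will occur". Anything else is left to "the direction of the FDA and Mayo (and other participating institutions) IRB". The section states that it covers patients on Fisetin or placebo.

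Section 4.4 restates the rule with differences. Its trigger is "If a severe adverse event (SAE) occurs at any time during administration of the drug regimen, a formal review will occur". It does not mention one-at-a-time enrolment, and after four events "either the dosing regimen revised or discontinuation of the study protocol will occur", so the regimen is changed and not merely reconsidered.

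The event terms do not agree. The abbreviation list has "SAE Serious Adverse Event/Serious Adverse Experience", but 4.4 attaches that abbreviation to severe. Section 9.3.3 defines severe as a grade of intensity: the event interrupts usual activity and typically needs drug or other treatment. Section 9.1.3 defines serious by outcome (death, life threat, hospitalization, disability).

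The definitions do not supply relatedness. Section 9.1.2 counts adverse events whatever their cause, and 9.1.3 counts every death. Other parts of the protocol do state attribution: the 10% death rule at the end of 9.6 is limited to treatment-related deaths, and 4.4.2 requires attribution to the investigational product before treatment is discontinued for a Grade 3 event.

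Section 5.8 keeps study personnel blinded, apart from those preparing the product. Section 9.8 gives the DSMB unblinded data. Neither 9.6 nor 4.4 sends the four-event hold to the DSMB.

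**The concern.** Every participant is an infected nursing-home resident aged 65 or over. The primary scale in section 2.1 runs through hospitalization, ventilation, end-of-life care and death. The deterioration the trial is designed to measure can therefore also trip its hold, in either arm. A pooled count of four cannot separate drug harm from disease, and blinded staff can apply only a pooled count.

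At stake is an interruption that carries no information about Fisetin. The outcomes named after it are a dosing change (considered in 9.6, made in 4.4) or discontinuation; resuming without change is not named. Two sites could also count differently, because the event is severe in one place and an SAE in another, and because the text does not say whether unrelated events count.

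**Working it through.** **Inputs**

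- Threshold: four events, trial-wide (9.6 and 4.4).
- Number randomized: 150, 75 per arm (3.2).
- Control distribution at Day 14: equal over seven categories, so 1/7 dead (8.1). This is a power input, not a forecast. With 75 per arm, an odds ratio of 2.25 and two-sided alpha 0.05, the Whitehead proportional-odds formula gives 80.3% power against the stated 80%, so 1/7 is consistent with the stated power.
- Event rate during the dosing window: not given anywhere. It is an assumption here and is shown as a range.

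The protocol states no operating characteristics for the hold rule, so there is no figure to reproduce for the rule itself.

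**Formula.** If the drug is inert, both arms share one per-patient probability p of at least one counted event in the window. With independent patients,

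P(hold) = P(X ≥ 4) = 1 − Σ(k = 0 to 3) C(150, k) p^k (1 − p)^(150 − k).

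For example, at p = 0.02 the terms for k = 0, 1, 2, 3 are 0.0483, 0.1478, 0.2248 and 0.2263. They sum to 0.6472, so P(hold) = 0.353.

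**Any-event rates (assumed)**

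| Rate in window | Expected patients with an event | P(at least 4) |
|---|---|---|
| 1% | 1.5 | 0.06 |
| 2% | 3.0 | 0.35 |
| 3% | 4.5 | 0.66 |
| 5% | 7.5 | 0.945 |

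Solving P(hold) = 0.5 gives p = 0.0244. Solving P(hold) = 0.10 gives p = 0.0117.

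**Deaths only, from the 1/7 in 8.1, applied to both arms**

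| Share of those deaths in the window (assumed) | p | P(at least 4) |
|---|---|---|
| All | 1/7 | above 0.9999 |
| Half | 1/14 | 0.995 |
| A quarter | 1/28 | 0.79 |

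Non-fatal severe events would add to these.

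**First step in 9.6.** Formal review and one-at-a-time enrolment need a single event: P = 1 − (1 − p)^150, which is 0.78 at 1% and 0.95 at 2%.

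**Would counting only related events cure it?** Section 9.3.2 grades an event Possible even if concurrent disease could also explain it. Let f be the share of in-window deaths graded at least Possible (assumed), and replace p by f × p:

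| f | p = 1/7 | p = 1/14 |
|---|---|---|
| 10% | 0.17 | 0.02 |
| 20% | 0.62 | 0.17 |
| 50% | 0.995 | 0.79 |
| 80% | above 0.999 | 0.97 |

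**Would a by-arm split of the four events be enough?** With an inert drug and 1:1 allocation, P(3 or more of 4 on Fisetin) = (4 + 1)/16 = 0.31. Four events are too few, so the by-arm review has to cover all deaths and SAEs to date.

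**Limits.** The calculation counts patients, while the rule counts events; repeat events in one patient would make a hold more likely.

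**The case against.** The strongest reply is that no document gives a Day 0 to 9 event rate. The 25 to 50% mortality in section 1.6 has no time frame, and the background in 1.1 dates from December 2020, while this is Version 7 of May 2023. Participants may be vaccinated and may receive standard COVID-19 treatment. Unstable major disorders are excluded. These facts point to lower rates, and at 1% the hold probability is only 0.06. This stands: a reader might infer that the hold will probably be reached, but the documents do not support that without a rate above about 2.4%. The broad definition of severe in 9.3.3 makes such a rate plausible; it does not establish it.

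Second, the intent may have been to count related events only. Section 9.2 limits immediate reporting to events at least possibly related, and 9.3.1 sends only directly related events to the IRB. That intent is plausible, but those filters govern reporting and do not amend the trigger. Where the protocol wants attribution in a rule, it writes it, including in the next rule of 9.6.

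Third, patients are protected. The DSMB is independent, sees unblinded data, meets monthly or as NIH decides, and may recommend stopping for excess SAEs. The reviewers in the formal review are not named, so DSMB involvement is not excluded, and 9.7 calls for a data and safety-monitoring plan that might settle the route. This stands as to safety. It does not tell anyone applying 9.6 or 4.4 what to do at the fourth event.

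Fourth, a sensitive hold can be a deliberate conservative choice for a pilot in frail people. That is fair, and it is a reason to keep the threshold of four and change what follows it.

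**Conclusion.** The point holds as a defect in the definition and routing of the rule, with a conditional size. The trigger pools both arms, has no relatedness condition or denominator, names the event inconsistently and is not linked to the only body that sees data by arm. Taken literally, with an inert drug and 150 patients, a hold is more likely than not above a per-patient rate of about 2.4% in the dosing window and has probability below 0.10 under about 1.2%. This rests on independent patients, a common rate in both arms and an event rate that the documents do not give.

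Two stronger readings should be set aside. The rule does not end the trial automatically: the stated consequence is a hold, and 9.6 only has an alternative regimen considered, although 4.4 is stricter. Nor is the trial without by-arm safety review, since 9.8 provides it; the gap is that the hold is not tied to it. The cost is an uninformative interruption, not unprotected patients or a biased primary analysis. It should be fixed; confidence is medium because the size depends on an unstated rate.

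**What to change.** Make the same changes in sections 9.6 and 4.4:

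1. Use one event term throughout, for example a serious adverse event as defined in 9.1.3, and remove the severe/SAE mixture.
2. Make the fourth event a pause with unblinded by-arm review by the section 9.8 DSMB, covering all deaths and SAEs to date and not only the four.
3. List resumption without change as an outcome, beside a regimen change and discontinuation.

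The second change is the essential one. Restricting the count to related events is optional and should be left to the DSMB, FDA and IRB: it loosens a safety trigger through attribution made blind, and the figures above show that it can still produce false pauses.

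The cost is a protocol amendment with IRB review. No new data are needed, because the DSMB already receives unblinded data. There are two downsides. The hold would no longer lead by default to a regimen change or discontinuation. If serious is the chosen term, severe non-serious events would leave the automatic count, so they should still go to the DSMB for by-arm comparison.

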### 9.7 Medical Monitoring

It is the responsibility of the Principal Investigator to oversee the safety of the study. This safety monitoring will include careful assessment and appropriate reporting of adverse events as noted above, as well as the construction and implementation of a data and safety-monitoring plan (see section 11 "Study Monitoring, Auditing, and Inspecting"). Medical monitoring will include a regular assessment of the number and type of serious adverse events.

